This clinical study was a 3-month prospective, single-center trial. Obese adults aged 18-65 years were recruited. After signing the informed consent, patients meeting the inclusion/exclusion criteria who completed baseline clinical visits and data collection were randomly assigned 1:1 to the intervention group (n=30). The intervention group was treated with low LA diet pattern for 12 weeks.

Intervention measure

Low LA nutritional diet description: The fat intake is mainly unsaturated fatty acids (such as linseed oil, olive oil, etc.), and the diet structure includes a diet containing fruits, vegetables

and grains, fish, shrimp and seafood, poultry and eggs. Cooking dishes using olive oil, reduce the intake of LA, can eat a moderate amount of nuts; Eat a small or moderate amount of yogurt or cheese every day; Appropriate intake of fish, shrimp and seafood; Eat eggs; During the intervention period, try not to consume red meat (cattle, sheep, pork); Drink the right amount of water every day.

Intervention process

1. For 12 weeks, the intervention group used olive oil for cooking, caloric restriction, 1300Kcal for women and 1600Kcal for men. A trained professional dietitian evaluates the menu weekly to limit LA intake.
2. At baseline visits, trained physicians conducted face-to-face interviews using standard questionnaires to obtain information on demographic attributes, lifestyle factors, health status and drug use.
3. Study participants were asked not to change their physical activity and to continue their chronic medications unless modified by their personal physician.
4. To help improve adherence to allowable caloric intake, all participants received dietary counseling throughout the duration of the trial. Dietary counseling is conducted under the guidance of a trained nutritionist. Participants received a written diet information brochure with some suggestions and sample menus.
5. At the beginning of the intervention, each participant was trained. The patients self-measured their fasting weight every day and recorded their sleep, step count and dietary adaptation.
6. Participants received weekly online healthy eating promotion training to guide them on how to firmly specify their diet for a long time, ensure the quality of their diet, and avoid overeating when they eat freely, to assess participants' adherence to the program and help participants achieve their caloric goal of weight loss within 3 months.

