7. The participants measured their neck circumference, waist circumference and hip circumference at the end of each week and gave feedback on their eating situation.
8. in week 4 and week 8, the subjects were followed up in the outpatient department for biochemical examination, in body test, face-to-face communication with doctors to evaluate the effect of weight loss.
9. At baseline and at week 12, gastric tissue specimens were collected for gastric injury assessment.
10. Compliance is assessed by dividing the number of meals served by the number of meals served.
11. Physical examination, biochemical and imaging examinations were performed on all participants at the 12th week.

Subject population

The inclusion criteria were:

- (1) Men and premenopausal women, aged 18-65 years at the time of signing the informed consent
- (2) Obese patients were diagnosed based on body mass index (BMI) 28-40kg/m²

2. Exclusion criteria are:

- 1) Patients who do not have or lose the ability to make autonomous judgments, do not understand the purpose of the study, or are unwilling to cooperate;
- 2) Heart, liver, kidney dysfunction and systemic diseases, such as various malignant tumors, systemic allergic diseases, autoimmune diseases;
- 3) Drug or alcohol dependence, intellectual disability, mental disorders;
- 4) Pregnant and lactating women;
- 5) Confirmed *Helicobacter pylori* infection (PPI, bismuth and antibiotics were stopped for at least 4 weeks, and any of the following tests were positive: non-invasive Hp test such as urea breath test, monoclonal stool *Helicobacter pylori* antigen test, serum soluble *Helicobacter pylori* antigen test; Invasive Hp test included rapid urease test and tissue section staining);
- 6) diagnosis of acute gastric mucosal lesions;
- 7) According to the Consensus Opinion on Chronic Gastritis in China in 2017, the patient was diagnosed with chronic gastritis according to the new Sydney system visual simulation scoring method and the pathological diagnostic criteria of chronic gastritis in China;
- 8) Patients with gastroscopy and histological pathology who meet the diagnostic criteria for gastric ulcer
- 9) the Diagnosis and Treatment of Gastric Cancer, combined with endoscopic, histological and imaging examinations, adenocarcinoma was diagnosed

Termination criteria

Discontinue use of the test product in any of the following cases:

The subject requests withdrawal of informed consent

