Inclusion in trials that violated inclusion and/or exclusion criteria and/or randomization criteria

Safety concerns are at the discretion of the investigators

Subjects will not tolerate serious adverse events

Excessive alcohol consumption (>70 g/wk) and smoking habits

Diagnosed with cancer, kidney disease or diabetes, lactose intolerance

Pregnant or trying to get pregnant

To participate in a clinical trial of another approved or unapproved investigational drug product

Research process

Screening period

Potential participants were recruited through advertising

All subjects are required to complete relevant screening tests before enrollment and be screened according to the admission criteria

Sc/Rz (Screening period) related content is as follows:

sign informed consent;

Demographic characteristics: sex, age

Medical history: including past medical history and drug use history

Physical examination: height and weight

Baseline Period

V0 (baseline period) : Subjects who meet the inclusion criteria and do not have exclusion

criteria can be directly enrolled.

V0 (baseline period) related content is as follows:

Physical examination: height and weight

Laboratory tests: glucose metabolism, lipid metabolism, thyroid function, liver and kidney function

Laboratory examination: liver and kidney function, glucose metabolism, lipid metabolism

Imaging examination: hardness data ultrasound

24 hour Dietary Review Scale

Gastric tissue assessment of gastric injury

Participants were provided with a written dietary information brochure containing some of the recommendations and sample menus

Intervention Period

Record the daily diet, collect and analyze the diet according to the weekly diet recall table.

in week 4 and week 8, the subjects were followed up in the outpatient department for biochemical examination, in body examination, face-to-face communication and evaluation with doctors

Participants' fasting weight was measured every morning, and the number of meals, eating time, eating feelings, sleep and step count were recorded.

The adverse reactions and severity during the intervention were recorded.

Healthy diet publicity and education: Online healthy diet training will be conducted once a week to promote regular and quantitative eating, avoid overeating, and ensure diet quality.

Endpoint Period (Week 12)

measurement same as base line

Statistical methods

Sample size estimation

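### Smoking and alcohol above 70 g/week stop the diet but do not bar entry, so on the plain reading an eligible patient can be randomised while already meeting a stopping rule.

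*Protocol*

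**What the plan says.** Under Termination criteria the protocol gives a list headed "Discontinue use of the test product in any of the following cases". One entry is "Excessive alcohol consumption (>70 g/wk) and smoking habits". The next is "Diagnosed with cancer, kidney disease or diabetes, lactose intolerance". A separate entry covers patients who should not have been enrolled: "Inclusion in trials that violated inclusion and/or exclusion criteria and/or randomization criteria".

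Under Subject population there are two inclusion criteria (sex, menopausal status and age; BMI) and nine exclusion criteria. None of the nine mentions smoking. The only one that touches alcohol is item 3: "Drug or alcohol dependence, intellectual disability, mental disorders".

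Entry depends on those two lists alone. Under Baseline Period, "Subjects who meet the inclusion criteria and do not have exclusion" criteria may be enrolled directly, and Research design randomises patients who meet the criteria and have finished the baseline visit and data collection. The screening content lists "Medical history: including past medical history and drug use history" but no smoking or alcohol item. Intervention process, item 2, describes a baseline interview that includes lifestyle factors, but ties no entry rule to the answers.

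**The concern.** A condition that ends treatment should either be ruled out at entry or be something that can only arise later. Smoking and drinking above a weekly amount are usually established before a trial starts. Because they appear only on the stopping list, the protocol as written can randomise a patient to the diet and then require the diet to stop because of something already true at baseline.

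The Calculation process section describes the control group as having no intervention, so the rule can withdraw the diet in one arm only. A patient who is stopped and still measured at week 12 belongs to the diet arm but contributes little or no diet effect, which pulls the comparison towards no difference. If investigators instead overlook the rule, each such patient is a protocol deviation. If they apply it by judgement, handling will differ from patient to patient.

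**Working it through.** The protocol gives no figure on this point to reproduce. The check is a comparison of the lists, followed by the arithmetic of dilution.

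**Comparison of the lists**

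| Trait | Bars entry? | Stops the diet? |
|---|---|---|
| Smoking | No | Yes |
| Alcohol >70 g/week, not dependent | No | Yes |
| Alcohol dependence | Yes (item 3) | Only through the alcohol limit or the entry-breach item |
| Pregnancy | Yes (item 4) | Yes |
| Malignancy, kidney disease | Yes (item 2) | Yes |
| Diabetes, lactose intolerance | Not named | Yes, if pre-existing diagnoses count |

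The entry-breach item does not close the gap, because a smoker breaches no entry criterion. If the line requires both habits together, the group shrinks to non-dependent patients who smoke and drink more than 70 g/week. They are still eligible and still meet the rule on day 0.

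**Inputs**
- Diet arm of 30: Research design, reading n=30 as the diet arm.
- Expected reduction 3.67 kg, SD 2.42: Calculation process.
- Assumed, not in the protocol: the number k stopped, the control loss c (0 to 1 kg), the time of stopping, and SD 2.42 in both arms.

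**Dilution.** Let D be the between-arm difference when nobody is stopped. If k diet-arm patients stop on day 0 and then change like controls, the expected difference is D × (1 − k/30). The relative loss is k/30, whatever the controls do:
- k = 1: 3.3%
- k = 3: 10%
- k = 6: 20%

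If the stop comes at week 4 and a linear effect up to then is kept, the loss per patient is (8/12)/30 = 2.2%.

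**In kilograms.** D = 3.67 − c, so one day-0 stopper costs 3.67/30 = 0.12 kg (c = 0) or 2.67/30 = 0.09 kg (c = 1).

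**Effect on power for weight.** Two-sample t-test, 30 per arm, two-sided 0.05, control SD 2.42, diet-arm SD √(2.42² + p(1−p)D²) with p = k/30:

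| k | Difference, c = 0 | Power | Difference, c = 1 | Power |
|---|---|---|---|---|
| 0 | 3.67 kg | 0.9999 | 2.67 kg | 0.988 |
| 1 | 3.55 kg | 0.9998 | 2.58 kg | 0.980 |
| 3 | 3.30 kg | 0.999 | 2.40 kg | 0.958 |
| 6 | 2.94 kg | 0.989 | 2.14 kg | 0.894 |

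The protocol states no expected effect on gastric injury, so only the relative loss k/30 can be carried over to that part of the primary endpoint, and only if it is compared as a mean change.

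**The case against.** The strongest reply is that a termination list is about what happens during the study. Most neighbouring items are of that kind: withdrawal of consent, intolerable serious adverse events, pregnancy, joining another trial. Pregnancy, malignancy and kidney disease stand on both lists, which suggests that the termination list covers at least some onset after entry. Smoking and alcohol share one undated line, so whatever doubt attaches to one attaches to the other. All of this stands, and it is why the point is limited to the plain reading. It does not remove the mismatch. The line carries no date, a habit is more naturally a standing trait than an event, and the entry-breach item shows that the list also holds matters fixed at entry. The conditions on both lists also show how the protocol treats a state that it wants barred at entry.

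A second reply is that Intervention process, item 4, gives dietary counselling to all participants, so it is unclear what controls receive. This also stands in part. It leaves open how closely a stopped patient would resemble a control, which makes the 1/30 figure conditional. It does not give the control arm a study diet to stop.

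A reader might infer that stopped patients will be lost, and set them against the 10% dropout allowance. The document does not support this: the rule ends use of the test product, not follow-up, and Intervention process, item 11, has all participants examined at week 12. A reader might also infer that the trial loses its power. With the assumptions above it does not: even 6 stoppers leave 0.89 to 0.99 for weight, against a planned 90%.

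**Conclusion.** The mismatch between the two lists is real and can be read directly from the protocol. As written, the stopping rule can take the diet away after randomisation because of a trait present at baseline, in a non-dependent patient who smokes or drinks more than 70 g/week, or who does both if the line requires both. It would be too strong to say that every smoker must be stopped, since an on-study meaning remains possible.

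The size is modest and conditional: 3.3% of the between-arm difference per day-0 stopper in an arm of 30, or about 0.1 kg of weight, if the stopped patient then changes like a control. How many patients would be affected cannot be derived from the protocol, so the counts of 1, 3 and 6 are illustrations only. The case for acting is that the stopping is foreseeable, confined to the diet arm and cheap to prevent.

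Diabetes and lactose intolerance raise the same question only if the line on diagnoses is meant to include those made before entry, which the text leaves unclear. For lactose intolerance the answer has practical weight, because the diet advice includes "Eat a small or moderate amount of yogurt or cheese every day".

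**What to change.** Before recruitment, do one of the following:

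1. Add smoking and alcohol above 70 g/week to the exclusion criteria, and check both in the baseline lifestyle interview before randomisation. Add the questions if the interview does not already contain them; the protocol names lifestyle factors only in general.
2. Keep the entry criteria as they are and limit the stopping item to smoking or drinking above the limit that begins after randomisation.

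Either way, state whether one habit is enough or both are needed. Say also whether the line on diagnoses covers those made before entry; if it does, align diabetes and lactose intolerance in the same way. Which traits should bar entry is for the investigators to decide.

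The cost is an edit to one or both lists and perhaps one or two interview questions. Option 1 also gives a slightly narrower population and slightly slower recruitment. Option 2 avoids that cost, but lets existing smokers and drinkers above the limit stay on the diet, which must be acceptable to the investigators.

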It has always been a very important link in clinical trials to select research objects through random sampling technology to determine what sample size is representative. Sample size estimation is related to the reliability, repeatability and efficiency of the research results, which reflects the balance between clinical significance and statistics. In any study, it is impractical to study the population as a whole. Sample size refers to the minimum number of test units (study individuals) determined by corresponding statistical methods under the premise of ensuring the reliability of research conclusions. In the actual research process, a group of participants is selected from the population. This group of participants can not only weigh all aspects of the trial to ensure the efficiency of the test, but also fully represent the overall population, and draw a conclusion for the overall population according to the final test results. Therefore, sample size estimation is one of the key links of clinical trials.

Statistically speaking, the main parameters that affect the sample size are: Class I error α , Class II error β or certainty of the experiment (1 to β), tolerance error γ , and population correlation information. Three factors are often considered in optimal parallel randomized controlled trials, namely, the size of the difference between the experimental intervention and the control intervention, the requirement for the accuracy of the trial, and the compliance of the test subjects. The sample size is calculated as follows:

$$n = \frac{2\sigma^2 \times f(\alpha, \beta)}{(\mu_1 - \mu_2)^2}$$

Where, n is the required sample size for each group, μ_1 is the basic measurement value, μ_2 is the measurement value to be reduced, σ is the standard deviation, $f(\alpha, \beta)$ is a constant, which can be obtained by looking up the table according to the difference between α and β . In test reports with explicit formulas, researchers often set Class I error α to 0.05 and Class II error β to 0.2. These parameters were originally set to avoid the problem of false positives and false negatives, and are not set in stone, but there are few reports to adjust the size of the parameters according to the actual situation.

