Relevant parameters: In general, sample size estimates are closely related to the target disease. Combined with the target disease of the test, the size of class I error α and class II error β are appropriately adjusted to ensure that the β is as small as possible when the α is sufficiently small, so as to maintain the rejection of H_0 and not make big mistakes. At the same time, it is necessary to clarify the relevant values of target diseases and target drugs. Such as: standard deviation σ , tolerance error γ , etc.

Compliance: For clinical trials, the shedding rate refers to the proportion of cases that failed to complete the trial according to the trial design after enrollment. For RCT, the shedding rate refers to the number of people who fail to complete the test. The total sample size required for the trial was $2n/(1-10\%)$ with 10% dropout or loss of follow-up considered.

· Calculation process:

A randomized controlled study was conducted to investigate plant-based diet intervention in obesity. Patients were divided into treatment group and control group (no intervention group) by completely randomized method. The main outcome indicator was the weight change of obesity after intervention.

The sample size was determined according to the weight change in the previous pre-experiment, and the weight index was a continuous variable. The average weight of the control group was expected to be 80.31 ± 15.63 (before intervention), and the weight of the intervention group was expected to be reduced by 3.67 ± 2.42 after the plant-based diet. For bilateral test, α was 0.05, the ratio of sample size between the two groups was 1:1, and the certainty (test efficiency) was $1-\beta=90\%$. PASS15 software was used to calculate the required sample size.

Safety monitoring, reporting and medical treatment

Definition of Adverse Events (AE)

An adverse event is any adverse medical event that occurs after a patient or subject receives a drug that is not necessarily causally related to the treatment. Therefore, an adverse event can be any adverse physical sign (including abnormal laboratory results), symptom, or disease that has a time correlation with the use of the investigational drug, regardless of whether a causal relationship with the investigational drug is considered. Adverse events include Serious adverse events (SAE) and non-serious adverse events.

SAE Definition

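### The sample-size calculation pairs a baseline weight level for controls with a weight change for the intervention group and reports no n, so the 90% power cannot be linked to the only n given, 30

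*Protocol*

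**What the plan says.** The Calculation process text under Sample size estimation names the sized outcome: "The main outcome indicator was the weight change of obesity after intervention". It describes two arms: "Patients were divided into treatment group and control group (no intervention group) by completely randomized method". Its numerical inputs are:

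- control group: "The average weight of the control group was expected to be 80.31 ± 15.63 (before intervention";
- intervention group: "the weight of the intervention group was expected to be reduced by 3.67 ± 2.42 after the plant-based diet";
- two-sided α of 0.05, 1:1 allocation and 90% power;
- 10% dropout, with the total given as 2n/(1−10%).

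The general formula earlier in the section is n = 2σ²·f(α,β)/(μ₁−μ₂)². There, "n is the required sample size for each group", μ₁ is the basic measurement, and μ₂ "is the measurement value to be reduced". It takes a single σ.

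The calculation stops at "PASS15 software was used to calculate the required sample size", and no n follows. The only group size in the protocol is in Research design: "randomly assigned 1:1 to the intervention group (n=30". No control-group size is given.

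**The concern.** A two-group comparison of weight change needs an expected change in each arm and an SD of change. The protocol gives the control arm a weight before treatment and the between-person SD of that weight. Neither is a change. The 2.42 is an SD of change, but for the intervention arm only. Zero control change is a plausible reading of a no-intervention group, but it is not stated. Item 4 of Intervention process gives dietary counselling to all participants, so zero is not a safe default.

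The formula does not settle which SD was used. Its description of μ₁ and μ₂ also fits a comparison of weight levels with σ = 15.63.

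The 90% is the protocol's only power figure. A reader who cannot reproduce it, or get from it to 30, cannot tell whether 30 per group gives more or less than 90%.

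**Working it through.** **Inputs.** From the protocol: difference 3.67 kg, SDs 15.63 and 2.42, two-sided α 0.05, power 90%, allocation 1:1, total 2n/(1−0.10). Assumed: zero control change, unless stated otherwise.

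**Constant.** f(α,β) = (1.960 + 1.2816)² = 10.507.

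**The protocol's formula with each SD it prints.**

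- SD 2.42 in both arms: n = 2 × 2.42² × 10.507 / 3.67² = 9.14, so 10 per group.
- One printed SD per arm: n = (15.63² + 2.42²) × 10.507 / 3.67² = 195.2, so 196 per group.
- SD 15.63 in both arms: n = 2 × 15.63² × 10.507 / 3.67² = 381.2, so 382 per group.

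The t-test gives 11, 197 and 383. For the mixed case the root-mean-square SD is √[(15.63² + 2.42²)/2] = 11.18.

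| SD used | Standardised difference | n per group | Total with 10% dropout | t-test power, 30 per group | t-test power, 27 per group |
|---|---|---|---|---|---|
| 2.42 in both arms | 3.67/2.42 = 1.52 | 10–11 | 23–25 | >99.9% | >99.9% |
| 15.63 and 2.42 | 3.67/11.18 = 0.33 | 196–197 | 436–438 | 24.0% | 22.0% |
| 15.63 in both arms | 3.67/15.63 = 0.23 | 382–383 | 849–852 | 14.5% | 13.5% |

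Other variants also fail to give 30 per group, or 27 before dropout:

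- 80% power: 7 (SD 2.42) or 285 (SD 15.63) per group.
- One-sided at 90% power: 8 or 311 per group.
- Paired design: 5 or 191.
- Literal difference 80.31 − 3.67: 1 to 3 per group.

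**Working back from 30.** Reading 30 as per group, the total is 60. Setting 60 = 2n/0.9 gives n = 27. The standardised difference that produces n = 27 is 0.88–0.90 by the formula and 0.90–0.92 by t-test. At 3.67 kg that means an SD of roughly 4.0–4.2 kg (for example 3.67/0.90 = 4.08), which is neither printed SD. Reading 30 as the total gives n = 13.5. By the formula that needs an SD of 3.67 × √(13.5/2) / 3.2415 = 2.94, which is not printed either.

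**What the two unstated inputs decide.** The t-test power with 27 evaluable per group is below. The control losses and the SDs of 3 and 4 kg are assumptions, as is using 2.42 for both arms.

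| SD of change | Control loss 0 kg | 1 kg | 2 kg |
|---|---|---|---|
| 2.42 | >99.9% | 97.8% | 70.1% |
| 3 | 99.3% | 89.4% | 51.9% |
| 4 | 91.1% | 67.3% | 32.5% |

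The difference detectable with 90% power at 27 per group is 0.899 SD. The control loss that still leaves 90% power is therefore 3.67 − 0.899 × SD: 1.49 kg at SD 2.42, 0.97 kg at SD 3 and 0.07 kg at SD 4.

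**The case against.** The strongest reply is that the text leans towards the change scale. Weight change is named as the outcome, the pre-experiment's weight change as the basis, and the primary endpoint is change from baseline. The 80.31 ± 15.63 is labelled as pre-intervention and may be only a baseline description. On that reading, with zero control change and SD 2.42 in both arms, the minimum is 10–11 per group. The protocol itself defines sample size as a minimum, so enrolling 30 contradicts nothing. If 30 were the total, 13 evaluable per group would still give about 96% power.

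Most of this stands. It rules out any claim that the trial is shown to be too small. It does not supply the link: a calculation that yields 10–11 does not explain 30, and it still depends on two inputs that are not stated.

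The large totals must also be read with care. The mixed case combines the SD of a level with the SD of a change and describes no coherent outcome. The 15.63 case sizes a comparison of levels, not of change. They show how far apart the printed figures can lead and are not estimates of this trial's power.

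Finally, 0.90 SD describes what 27 evaluable per group can detect. It does not show that a difference of that size matters.

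**Conclusion.** The concern holds. The sizing inputs are on different scales, the control change and a common SD of change are missing, no n is reported, and 30 does not follow from the printed figures. With the assumed zero control change, those figures give totals from 23 to 852 depending on the SD taken, and power with 30 per group from 14.5% to above 99.9%. The back-calculation to n = 27 rests on reading 30 as per group, the most natural reading of a garbled sentence; reading it as a total does not give a match either. The defect is a power statement that cannot be reproduced. A power shortfall is not demonstrated. It should be fixed, because whether 30 per group exceeds or misses 90% turns on the two unstated inputs.

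**What to change.** Restate the calculation on one scale, change in weight from baseline to week 12. Keep 80.31 ± 15.63 only as a baseline description, not as a sizing input. State:

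1. the assumed control change;
2. one common SD of change;
3. the resulting n per group, and the total from 2n/(1−10%);
4. the control-group n.

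Then reconcile the result with 30. If 30 per group is kept, replace the unlinked 90% with what that number delivers: with 27 evaluable per group, 90% power for a between-group difference of 0.90 SD of change. That is 0.899 × 2.42 = 2.18 kg, about 2.2 kg, only if the SD is 2.42 in both arms. Add why a difference of that size is worth detecting. Because Study endpoint also lists gastric injury as primary, say that this power applies to weight change only.

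The cost is protocol wording, with no added visits or procedures. Enrolment changes only if the restated inputs need more than 27 evaluable per group and 90% power is kept.

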SAE refers to the occurrence of medical events during clinical trials that require hospitalization or prolonged hospitalization, disability, affect work ability, endanger life or death, and lead to

congenital malformations. Includes the following medical events:

- 1) events leading to death;
- 2) life-threatening events (defined as subjects in immediate danger of death at the time of the event);
- 3) Events requiring hospitalization or prolonged hospitalization;
- 4) Events that can cause permanent or severe disability/disability/affect the ability to work;
- 5) Congenital abnormalities or birth defects;

Other medically important events (defined as events that endanger subjects or require intervention to prevent the occurrence of any of the above).

Adverse event recording, collection, reporting and handling

Collection and recording of AE

All aes that occur between the signing of the informed consent and the provision of the plant-based diet should be recorded in the CRF table.

The record of the AE should include: description of the AE and all associated symptoms, time of occurrence, severity, duration, correlation with the test food, action taken, and final outcome and outcome. The recording of AE must use medical terminology, and if the subject's signs and symptoms can be summarized by a common cause, the diagnosis should be recorded as far as possible. In addition to indicators related to disease progression, all clinical events and clinically significant laboratory adverse events can be treated with reference to the Common Adverse Event Evaluation Criteria (CTCAE) version 5.0. Adverse reactions to treatment will be recorded by the investigator.

Pregnancy

Women who are fertile should use an effective contraceptive method for the period specified in the study. Before recruiting fertile women into the study, researchers must inform women of childbearing age about the importance of avoiding pregnancy during study participation, as well as potential risk factors for unwanted pregnancies. Subjects must sign informed consent forms to show that the issues have been discussed and fully understood.

Pregnancy test requirements: Urine pregnancy test results must be negative for all fertile women during screening, baseline, and treatment. In addition, all fertile women should be advised to report a possible pregnancy (such as menopause or delayed menstruation) to the investigator immediately at any time during the trial.

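### The adverse-event definition depends on receiving a drug that this diet trial does not give, leaves non-serious control-arm events uncovered, and conflicts with recording from informed consent

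*Protocol*

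**What the plan says.** The section Definition of Adverse Events (AE) opens: "An adverse event is any adverse medical event that occurs after a patient or subject receives a drug". It does not require a causal link, but it does require timing: a sign, symptom or disease counts if it "has a time correlation with the use of the investigational drug".

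No study drug is described anywhere. Research design states: "The intervention group was treated with low LA diet pattern for 12 weeks". The Calculation process text under Sample size estimation adds: "Patients were divided into treatment group and control group (no intervention group) by completely randomized method". Item 9 of Intervention process places the biopsies: "At baseline and at week 12, gastric tissue specimens were collected for gastric injury assessment".

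Collection and recording of AE works from a different starting point. The events to be entered in the CRF are "All aes that occur between the signing of the informed consent and the provision of the plant-based diet", and the relationship item listed is "correlation with the test food", not relationship to a drug. SAE Definition describes serious events as medical events arising during the trial and sets no exposure condition. The Intervention Period text has adverse reactions and their severity recorded, without naming an arm. Pregnancy reporting again refers to a study drug.

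**The concern.** An adverse-event definition decides what site staff write down. Here it rests on an exposure that nobody in the trial has. The natural repair, reading drug as study diet, works for the intervention group only, because a control participant without intervention never receives the diet. Staff who follow the definition in that sense would record a minor event in a diet participant and could pass over the same event in a control participant.

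The definition and the collection rule also disagree about when an adverse event can first exist: after exposure in one, from consent in the other. The baseline gastric specimen falls in between, so two readers could treat a minor complication of it differently. At stake are the completeness of the safety record and whether it is gathered alike in both arms.

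**Working it through.** There is no stated figure to reproduce and no calculation to run. The check sets the sections side by side.

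**Inputs**

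1. Trigger in the AE definition: receipt of a drug, with a time link to the investigational drug.
2. Intervention (Research design): a 12-week diet; no drug.
3. Control (Calculation process): no intervention.
4. Gastric specimens (Intervention process, item 9): baseline and week 12. Research design puts consent before baseline data collection, and assignment after it, so the baseline specimen comes after consent and before the diet.
5. Collection rule (Collection and recording of AE): opens at consent and, as worded, closes at provision of the diet.
6. SAE Definition: no exposure condition.

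**Coverage by type of event**

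| Event | AE definition, literal | AE definition, drug read as diet | Other sections |
|---|---|---|---|
| Complication of baseline specimen, either arm | Not covered | Not covered (before the diet) | Covered by the collection rule, since it follows consent |
| Non-serious event in diet arm after the diet starts | Not covered | Covered | Intervention Period records adverse reactions |
| Non-serious event in control arm after randomisation | Not covered | Not covered (no exposure) | Not clearly covered |
| Complication of week-12 specimen, diet arm | Not covered | Covered | SAE wording, if serious |
| Complication of week-12 specimen, control arm | Not covered | Not covered | SAE wording, if serious |
| Serious event, either arm | Not covered | Diet arm only | Covered by the SAE wording |

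**Reasoning**

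- The literal column is empty for both arms. It makes the definition unusable but creates no imbalance.
- The diet reading creates the imbalance. The third row is the one that no other section clearly fills. The collection rule applies to adverse events, a term that leads back to the definition, and its closing point never occurs for a control participant. The Intervention Period text speaks of reactions and names no arm.
- The first row is a contradiction, not an omission: the collection rule has adverse events recorded in a period in which the definition allows none.
- The last row is a further mismatch. The AE section makes serious events a subset of adverse events, yet the SAE wording is wider than the AE definition.

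**Share of participants affected.** With 1:1 allocation, controls are 1/(1+1) = 50% of those randomised. The number of events involved cannot be derived, because the protocol gives no event rate.

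**The case against.** The strongest reply is that this is leftover template language. Other sections speak of a test product or test food, recording starts at consent, and serious events count whenever they happen, so sensible staff would record everything in everyone. Much of that stands, and it rules out three stronger readings that might be inferred.

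- *Baseline-biopsy complications cannot be adverse events.* That follows from the definition alone. The collection rule covers the period in which the baseline specimen is taken, so the document contradicts itself but does not exclude these events.
- *The control arm's adverse-event count is zero by definition.* The SAE wording has no exposure condition and reaches serious control-arm events.
- *A comparison of adverse events between arms will be biased against the diet by a stated amount.* The literal reading gives no difference between arms, the protocol plans no such comparison and lists no safety endpoint, and any risk difference would only restate an assumed background rate.

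It is also fair to say that the listed contents of an adverse-event record ("correlation with the test food, action taken, and final outcome and outcome" closes the list) are not declared exhaustive, and the CRF is not shown. It is therefore unproven that a procedural complication has nowhere to be attributed.

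The reply leaves one gap: it supplies no section that clearly covers non-serious events in control participants. The protocol relies on staff to disregard its definition. Nor does the uneven description of the control arm help. Research design names only the intervention group, and item 4 of Intervention process gives dietary counselling to all participants, but counselling is not the study diet.

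**Conclusion.** The point holds in this form: the adverse-event definition does not fit the trial, omits non-serious control-arm events once drug is read as diet, and contradicts the consent-based collection rule. Its size is a class of events, namely non-serious events after randomisation in half of the participants, together with an unsettled status for minor complications of the baseline specimen. Safety recording would be incomplete and could differ between arms; nothing firmer can be put in numbers.

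The conclusion assumes that the trial has the no-intervention control described in the sample-size text and that no unshown CRF instruction overrides the definition. It belongs in the protocol, because the protocol itself states the definition. The change should be made, since it is nearly free, but nothing here shows that efficacy results would be affected.

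**What to change.** Reconcile Definition of Adverse Events (AE), Collection and recording of AE, and Pregnancy reporting so that they refer to the same exposure and the same participants.

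- Define an adverse event as any untoward medical occurrence in an enrolled participant of either arm, from informed consent onward, whether or not related to the study diet or a study procedure.
- Remove the drug and investigational-drug wording from the AE definition. The study-drug wording under Pregnancy reporting needs to be reconciled with a trial that gives no drug; what that rule should require is for the investigators to settle.
- Use the same adverse-event form in both arms.
- Optionally, let the relationship item cover study procedures as well as the test food.

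The collection window's closing point is a related but separate matter. As worded it does not clearly span the 12 weeks of diet, and correcting it alone would leave the exposure condition in place.

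The cost is protocol wording and, if the option is taken, one CRF item. No visit or procedure is added. The small downside is more control-arm and procedure-related events to record.
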